STATISTICAL PLAN**Time-based Register and Analysis of COPD Endpoints (TRACE).****NCT number:** NCT03485690**Date:** February 2nd, 2018**Scientific committee:**

[name]

[name]

[name]

[name]

[name]

[name]

Institutions:

(1) Centro de investigación biomédica en red de enfermedades respiratorias (CIBERES).

Instituto de Salud Carlos III, Madrid Spain

(2) Unidad Médico-Quirúrgica de Enfermedades Respiratorias, Instituto de Biomedicina de

Sevilla (IBiS), Hospital Universitario Virgen del Rocío/Universidad de Sevilla, Seville,

Spain

Statistical plan

The data will be analyzed using the software IBM SPSS Statistics (IBM corporation, Armonk, New York). For the description of the variables, centralization and dispersion estimators appropriate to the nature of each variable and its distribution will be used. The differences between baseline patient types will be analyzed using the Student's t test for independent data (after checking the equality of the variances with the Levene test) or using the Chi-square test (with Fisher's correction if applicable) for qualitative variables. Follow-up studies will be done using the Student's t test for paired data or with the McNemar test for categorical variables. Potential associations found in this bivariate analysis will be further evaluated via a multivariate study depending on the nature of the analysis. Accordingly, the calculation of the relative risk of future events will be adjusted from multiple regression models. Survival analysis will be carried out by Kaplan-Meier curves with log-rank test to assess differences between potential patient groups. Potential associations will be further explored by Cox proportional hazards regression analysis. The level of statistical significance is set at 0.05.

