Since the main objective of the project is to generate a cohort of patients, the total number of patients seen in one of our COPD-dedicated outpatient clinics during the year were to be selected through our electronic medical records system (SIDCA) at our institution. The number of patients seen for a consultation, in a year, is estimated at around 15 patients a day, for 4 days a week, for 48 weeks a year, a total of 2880 cases. Of these approximately 20% have alternative diagnosis to COPD, 20% are discharged at the first visit and we estimate a 10% loss

in follow-up. For this reason, we estimate an initial cohort of patients from 1440 cases with a minimum follow-up of 3 years.

Protocol

To include new cases, a retrospective review of patients who meet the inclusion / exclusion criteria will be done. For this, proceed as follows: the COPD-dedicated outpatient clinic of the principal investigator will be reviewed to evaluate all the patients that were evaluated in this consultation. Once identified, those who are still in follow-up will be selected and the data will be collected for inclusion. Subsequently, the patients included will be followed up prospectively with annual visits until their death or loss of follow-up, as per clinical practice in our institution.

Outcome measures

Primary outcome measures will be survival. Secondary outcomes measures include:

- Symptoms perception: dyspnea measured by mMRC scale (19)
- Number of moderate or severe exacerbations, defined as in the GOLD document (20)
- Time to first moderate or severe exacerbation
- FEV₁ annual decline
- Forced expiratory flow at 25-75% of expiration (FEF25-75)
- Peak expiratory flow (PEF)
- Peripheral blood eosinophils count expressed in cells/ μ L and in percentage of the white cell count
- Serum Alpha1-antitrypsin
- Total IgE
- Positive bronchial colonization
- Inhaled and oral COPD-related medication use

Registered data

The clinical data that will be collected at each annual visit include:

Filiation data:

- Gender
- Birth date

Previous history:

- - Smoking history
- - Comorbidities, collecting 4 indices: Charlson (21), COTE (22), COMCOLD (23) and Functional Comorbidity Index (24).
- History of COPD: type of disease according to GOLD (11) and the Spanish guideline: GesEPOC (18), updating the database with subsequent updates of these documents.

Current Anamnesis:

- Current symptoms: dyspnea according to the mMRC scale (19), cough, expectoration, self-listening wheezing

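### Levene pre-testing before the baseline t test lets the false-positive rate exceed 5% when the smaller patient type is also the more variable; Welch's test, with logs for skewed variables, is a cheap improvement

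*SAP*

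**What the plan says.** The SAP (Statistical plan) states: "The differences between baseline patient types will be analyzed using the Student's t test for independent data", and adds in brackets "after checking the equality of the variances with the Levene test". Qualitative variables go to chi-square or Fisher. The overall level is given as "The level of statistical significance is set at 0.05", without sidedness.

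The SAP does not state the level at which Levene is judged, which test is used when Levene rejects, what is done with more than two patient types, or how skewed continuous variables are handled in these comparisons. It does say that associations suggested by the bivariate step are examined further in multivariable models.

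The protocol (Registered data) records disease type by the GOLD and GesEPOC classifications, but gives no expected size or SD for any type. The only design figure is in Sample size: "we estimate an initial cohort of patients from 1440 cases with a minimum follow-up of 3 years". The continuous variables include, under Outcome measures, "Peripheral blood eosinophils count expressed in cells/ μ L and in percentage of the white cell count" and total IgE.

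**The concern.** A rule that tests variances first and then picks the t test is a two-stage procedure, and its error rate is not that of either test alone. When Levene fails to reject, the pooled test is used even if the variances differ. Pooling is then dominated by the larger group. If the smaller group is the more variable, the standard error is too small and the test rejects too often; if it is the less variable, the test rejects too seldom.

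A large cohort does not by itself cure this, because Levene's power is limited by the smaller group. Patient types in an unselected clinic cohort have no reason to be equal in size or in spread. At stake is whether a baseline comparison reported at 0.05 has that error rate, and so how reliable it is as a pointer to associations worth modelling.

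**Working it through.** **Inputs.** From the documents: level 0.05 (two-sided assumed), Student's t test after Levene, cohort 1440. Assumed, because the documents are silent: Levene mean-centred at 0.05; Welch if it rejects and pooled otherwise (the gated rule below); sizes and SD ratios as shown. Ratios are small type over large type.

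**1. The plan's own figure.** 15 × 4 × 48 = 2880 cases, and 2880 × (1 − 0.20 − 0.20 − 0.10) = 1440. This matches the protocol. No power, group size or SD is stated for the t tests, so there is nothing further to reproduce.

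**2. Mechanism, worked for 72 vs 1368 (5% of 1440) at SD ratio 1.3.**
- Pooled variance: (71 × 1.69 + 1367) / 1438 = 1.0341
- Variance the pooled test uses: 1.0341 × (1/72 + 1/1368) = 0.01512
- True variance of the difference: 1.69/72 + 1/1368 = 0.02420
- Ratio of standard errors: √(0.01512 / 0.02420) = 0.790
- Effective critical value: 1.96 × 0.790 = 1.549, which a standard normal exceeds in absolute value with probability about 0.121

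Simulation gives 12.0% for the pooled test. Levene rejects in 83% of samples, so Welch is usually used and the gated rate falls to 5.9%, against 5.2% for Welch alone. The excess comes from the samples in which Levene does not reject.

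**3. Simulated false-positive rate, normal data, equal means.** Most runs used 20,000 replicates (standard error about 0.15 points at 5%). Ranges are across repeated runs.

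| Small vs large | SD ratio | Gated rule |
|---|---|---|
| 20 vs 200 | 1.3 | 8.0–8.6% |
| 30 vs 300 | 1.3 | 7.3–7.7% |
| 50 vs 700 | 1.2 | 6.8–7.3% |
| 72 vs 1368 | 1.2 | 6.5–6.8% |
| 100 vs 1340 | 1.2 | 5.7–6.2% |
| 144 vs 1296 | 1.2 | 5.8% |

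Welch throughout stayed between 4.7% and 5.4% with normal data.

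With the total fixed at 1440, the gated rate at SD ratios 1.25, 1.5 and 2.0 was:
- n=10: 9.7%, 11.3%, 8.6%
- n=20: 8.9%, 7.9%, 5.6%
- n=30: 7.8%, 6.4%, 5.1%
- n=72: 6.4%, 5.0%, 5.1%
- n=144: 5.2%, 5.1%, 5.0%

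From n=20 up, the excess fades as the ratio grows, because Levene then detects the difference.

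**4. The other directions (total 1440).** Equal variances: 5.0–5.4%. Small type less variable (ratio 0.8): 3.4% at n=10, 3.6% at n=30, 4.4% at n=72. If the pooled test were kept whatever Levene showed, which the SAP wording does not exclude, the error would be larger: about 19% at n=10 and 17.9% at n=72, both at ratio 1.5.

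**5. Cost of Welch.** Equal variances, total 1440, difference set for about 80% pooled power:

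| n in small type | Gated | Welch |
|---|---|---|
| 10 | 79.1% | 70.3% |
| 20 | 79.3% | 75.9% |
| 30 | 79.7% | 77.3% |
| 50 | 80.0% | 78.8% |
| 72 | 80.0% | 79.2% |
| 144 | 80.2% | 80.2% |

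**6. Skewed data.** False-positive rate with lognormal data (log-SD 0.7, an assumption), equal variances, total 1440:

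| n in small type | Gated | Welch, untransformed |
|---|---|---|
| 10 | 3.1% | 10.5% |
| 20 | 4.1% | 9.1% |
| 30 | 4.5% | 7.8% |
| 72 | 4.8% | 6.4% |
| 144 | 5.0% | 5.8% |

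The log of a lognormal variable is normal, so Welch on the log scale returns to the normal-data behaviour in step 3.

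**The case against.** The strongest reply is that this is a preference between two common procedures, and that the larger percentages need a particular combination: a small type, the larger spread in that type, and an SD ratio in the band Levene tends to miss. No document says that any such type exists. The 20 vs 200 and 30 vs 300 cases total 220 and 330 patients, not 1440. That stands as a limit on size. It does not remove the point, since at the full 1440 a type of 20 or 30 patients still gives 8.9% or 7.8% at ratio 1.25.

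A reader might infer three stronger things that do not hold:
- *That unequal size alone inflates the error.* It does not. With equal variances the gated rule is at about 5%, and with a less variable small type it is below 5%.
- *That Welch is free and can be used on every variable as it stands.* With very small types it loses power, and on untransformed skewed data it can exceed 5% where the gated rule does not.
- *That these p-values decide what enters the multivariable models.* The SAP says only that potential associations will be evaluated further. It states no entry rule at 0.05.

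**Conclusion.** The point holds as a cheap improvement of small size. The Levene step leaves the baseline t tests without a fixed error rate: above 5% when the smaller type is the more variable and Levene misses it, below 5% in the reverse case, and about 5% when variances are equal. At assumed ratios of 1.2 to 1.3 the excess is about 3 points for types of 20 to 30, about 1.5 for 72, and about 1 or less for 100 to 144.

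This rests on normal data, a switch to the unequal-variance test after rejection, and assumed sizes and SDs. If the pooled test is kept regardless, the excess is larger.

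A reader might infer that the trial's main conclusion is at risk. The documents do not support that: the primary outcome is survival, analysed by Kaplan-Meier, log-rank and Cox models, none of which uses this step. The effect is confined to exploratory baseline comparisons that point to associations for later modelling.

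**What to change.** Replace the Levene clause with wording to this effect: *Continuous baseline variables will be compared between two patient types with Welch's unequal-variance t test, and between more than two with Welch's ANOVA. Markedly skewed positive variables, such as eosinophil counts and total IgE, will be log-transformed first and reported as ratios of geometric means.* The skew of those two variables is an assumption, so list the variables to be transformed in advance, with a rule for zero values.

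This also settles what happens after a Levene rejection and how more than two types are compared. It needs no new data, only SAP wording. There are two costs. With equal variances, power falls by about 10 points at 10 patients in the small type, 2 to 3 at 20 to 30, and about 1 or less from 50. On the log scale, the comparison concerns geometric rather than arithmetic means.

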However, COPD is a dynamic disease that evolves over time. Hence, research projects are needed to evaluate the behavior of the disease over time and allow clinicians to learn, longitudinally, how the disease behaves and what are the determinants that influence its clinical presentation and response to the treatments. For example, from the functional point of view, it is possible that other functional markers provide relevant information on the evaluation of the patient with COPD. In addition, other markers, such as peripheral blood eosinophils, have been proposed as a marker of response to various treatments (16). In this sense, cohort studies play an essential role (8, 17).

The TRACE project (Time-based Register and Analysis of COPD Endpoints) is part of this line of prospective and longitudinal observational study of patients with COPD with the idea of generating a cohort of patients who provide relevant information on the multidimensional behavior of the disease over time and the determinants of the different response to treatments. The added value that tries to provide TRACE over other previous cohorts is to observe the multidimensional impact of the disease over time, but using tools that are of the

usual clinical practice and that are available to all clinicians. In this way, its conclusions may be applied directly to the patient with COPD. The present document describes the full methodology of TRACE.

Methodology

TRACE is a prospective observational cohort study that will include patients diagnosed with COPD and followed up by our monographic COPD-dedicated outpatient clinic since 2012.

Inclusion criteria

Patients evaluated in the COPD-dedicated outpatient clinic since the year 2012 will be selected for longitudinal follow-up. The inclusion criteria are:

- Adult patients, both genders
- Aged 40-90 years.
- Diagnosed of COPD, according to the current recommendations (11, 18).
- Evaluated in our COPD-dedicated outpatient clinic since 2012
- Followed up by our team for at least 3 years.

Exclusion criteria

Another relevant comorbidity that conditions their care, as judged by the research team.

Sample size

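### For repeated lung function, symptom and laboratory values the SAP names only two-visit tests, and FEV1 annual decline has no stated visits, estimation method or model

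*SAP*

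**What the plan says.** The SAP is one paragraph. For within-patient change it states: "Follow-up studies will be done using the Student's t test for paired data or with the McNemar test for categorical variables". Associations found in the bivariate work are to be "further evaluated via a multivariate study depending on the nature of the analysis", and the next sentence gives regression a specific purpose: "the calculation of the relative risk of future events will be adjusted from multiple regression models". Kaplan-Meier, log-rank and Cox methods are assigned to survival.

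The protocol (Outcome measures) lists FEV1 annual decline as a secondary outcome by name only. Dyspnoea on the mMRC scale, FEF25-75, PEF, eosinophils, alpha1-antitrypsin and total IgE are listed beside it. Under Registered data, the same information is gathered at each annual visit. Under Protocol, visits continue until death or loss to follow-up.

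The Inclusion criteria require patients to be "Evaluated in our COPD-dedicated outpatient clinic since 2012" and "Followed up by our team for at least 3 years". The Sample size section expects "1440 cases with a minimum follow-up of 3 years". The SAP is dated "February 2nd, 2018".

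**The concern.** A paired t test or McNemar test uses two measurements per patient, whereas the cohort supplies at least a baseline and three annual visits, and often more. The SAP does not say which two visits are compared. The outcome's name implies a per-year quantity, but nothing says how it is to be estimated or which visits contribute.

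The choice matters because follow-up is unequal by design. A fixed early pair ignores all later visits. A fixed later pair drops patients who have died, left or not yet reached that visit. If the pair is not named in advance, it can be chosen after the results are seen. The project aims to find determinants of how the disease behaves over time, so lost precision falls on comparisons of decline between patient types. Survival and exacerbation events have their own methods and are not in question.

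**Working it through.** **The plan's own figure.** 15 × 4 × 48 = 2880 consultations; 2880 × (1 − 0.20 − 0.20 − 0.10) = 1440. The stated cohort size reproduces. It is a feasibility count, used below only to scale precision.

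**From the documents.** Annual visits; entry from 2012; at least 3 years of follow-up; SAP date early 2018. Follow-up at that date therefore runs from 3 to about 6 years.

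**Assumed, because the documents give no values.** Between-patient slope SD b = 40 mL/yr (30 to 50); residual SD s = 120 mL (80 to 200); deaths m = 7% a year after year 3 (5 to 10%); entry uniform, so that one third of patients each have a last scheduled visit at year 3, 4 or 5; 80% power; two-sided 0.05. Losses other than death are left out.

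**Step 1: same interval.** With visits at years 0 to K:
- first-to-last slope variance = b² + 2s²/K²
- least-squares slope variance = b² + s²/Sxx, with Sxx = 5, 10 and 17.5 for K = 3, 4 and 5

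| K | s = 80 | s = 120 | s = 200 |
|---|---|---|---|
| 3 | 1.05 | 1.07 | 1.09 |
| 5 | 1.07 | 1.14 | 1.24 |

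The entries are first-to-last variance divided by all-visit variance at b = 40. The loss is small.

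**Step 2: all visits at the SAP date** (b = 40, s = 120, m = 7%). Shares by last visit:
- year 3: (1 + 0.07 + 0.07)/3 = 0.380
- year 4: (0.93 + 0.93 × 0.07)/3 = 0.332
- year 5: 0.93²/3 = 0.288

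Per-patient slope variances are 1600 + 14400/5 = 4480, 1600 + 14400/10 = 3040 and 1600 + 14400/17.5 = 2423. The weighted mean is 0.380 × 4480 + 0.332 × 3040 + 0.288 × 2423 ≈ 3409.

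**Step 3: fixed pairs.**
- Year-3 pair: 1600 + 2 × 14400/9 = 4800, and 4800/3409 = 1.41. Over all the assumed ranges this is about 1.2 to 1.7. Nobody is lost to death, because entry requires 3 years of follow-up.
- Year-5 pair: 1600 + 2 × 14400/25 = 2752 per patient kept, but only 28.8% are kept. Per patient enrolled this is 2752/0.2883 = 9546, and 9546/3409 = 2.80 (2.3 to 3.4 over the ranges).

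**Step 4: detectable difference in decline, two equal groups of 720.** 2.80 × 2 × √(v/1440):
- all visits: v = 3409 gives 8.6 mL/yr
- year-3 pair: v = 4800 gives 10.2 mL/yr
- year-5 pair: v = 9546 gives 14.4 mL/yr

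**Step 5: a later analysis date.** If every survivor has reached year 5 and the analysis stops there, the last-visit shares become 0.07, 0.93 × 0.07 and 0.93². The all-visit variance is then 2607. The year-3 pair gives 4800/2607 = 1.84 and the year-5 pair (2752/0.8649)/2607 = 1.22. The order of the two pairs reverses, so the cost depends on the analysis date as well as on the pair.

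**Step 6: selection.** Assume a mean slope of −40 mL/yr and a death hazard multiplied by exp(0.5) per SD of faster decline. Among patients who reach year 3 the mean slope is −35.89; among those also alive at year 5 it is −33.39. Decline is understated by 2.5 mL/yr. With the link reversed the values are −44.11 and −46.61, an overstatement of 2.5. With no link the bias is zero.

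**The case against.** The strongest reply is that the plan is open rather than wrong. Further modelling that depends on the nature of the analysis does not exclude a mixed model, and a short SAP is common for an observational registry. That is fair as far as it goes: the right method is not ruled out. But no model is named, the sentence that follows ties regression to the risk of future events, and the only methods actually named for follow-up use two occasions.

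A second reply is that a paired test is valid. It is, at a stated interval. Over the same interval the loss in precision is slight, and a year-3 pair has no bias from death in this cohort. The case rests on unused later visits and an unstated choice, not on invalidity.

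A reader might infer that raw first-to-last differences would be reported as annual decline, so that an assumed −40 mL/yr would appear as −120 mL in one patient and −240 mL in another followed for 6 years. The documents do not support this. The outcome is named as an annual quantity, and dividing by elapsed time removes the contrast.

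A reader might also infer that a later pair is the better compromise, at 1.22 times the all-visit variance against 1.84 for year 3. That holds only once every survivor has reached year 5. At the SAP date the year-5 pair is much the worse of the two.

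**Conclusion.** The point holds as a gap in specification with a moderate cost. That the SAP names only two-occasion tests for repeatedly measured variables, and that FEV1 annual decline has no stated visits, estimation method or model, follows from the text and needs no assumption.

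The size does rest on assumptions. At the SAP date, with uniform entry, a fixed pair costs about 1.4 times the all-visit variance (year 3) or about 2.8 times (year 5). In detectable difference this is 10.2 or 14.4 mL/yr against 8.6. Slope SD, residual SD, death rate and entry pattern are all assumed, and no document proposes either pair.

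It would go too far to say that the plan yields a biased decline. Bias in a later pair needs a link between leaving and rate of decline, and can run either way. The protocol says "we estimate a 10% loss" in follow-up but not who leaves. The primary survival analysis is unaffected. The change should be made, but the study does not depend on it.

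**What to change.** Define FEV1 annual decline as a per-year slope from all annual visits, using actual time since a stated baseline. State the unit, whether pre- or post-bronchodilator values are used, and the minimum number of measurements.

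- **Main analysis:** compare per-patient all-visit slopes between patient types with the independent t test already in the SAP, or with regression where adjustment is needed.
- **Sensitivity analysis:** a linear mixed model with random intercept and slope, and group-by-time terms for the determinants.
- **Other outcomes:** the same approach for FEF25-75 and PEF, and for continuous laboratory values where change is of interest; GEE or mixed logistic or ordinal models for repeated categorical or ordinal outcomes such as mMRC.
- **Paired t and McNemar:** descriptive only, naming the visit pair and the number of patients excluded.

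The cost is SAP wording and modest extra analysis, with no new data. Neither model is free of drawbacks. In a simulation under the Step 6 link, with follow-up to year 5 and deaths as the only loss, the mixed model was off by about 0.8 mL/yr and the mean of per-patient slopes by under 0.1, at about 4% higher variance (2524 against 2433). Neither corrects for the selection of patients who had to complete 3 years to enter.

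### The SAP describes adjustment only for associations that appear in crude tests and gives a crude-null factor no route into an adjusted model, so a factor masked by confounding may be missed

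*SAP*

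**What the plan says.** The SAP's Statistical plan is a single paragraph. It lists unadjusted tests: the independent t test and chi-square or Fisher for comparing types of patient at baseline, and the paired t and McNemar tests for follow-up. It then states: "Potential associations found in this bivariate analysis will be further evaluated via a multivariate study depending on the nature of the analysis".

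The next sentence concerns outcomes: "Accordingly, the calculation of the relative risk of future events will be adjusted from multiple regression models". It sets no condition of its own; only its opening word ties it to the bivariate step.

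For survival, the primary outcome under the protocol's Outcome measures, the SAP says "Survival analysis will be carried out by Kaplan-Meier curves with log-rank test to assess differences between potential patient groups" and then "Potential associations will be further explored by Cox proportional hazards regression analysis". The closing sentence is "The level of statistical significance is set at 0.05". That is a general level, not a stated criterion for entry to a model.

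The protocol's Methodology describes the design: "TRACE is a prospective observational cohort study that will include patients diagnosed with COPD". Under Registered data it collects sex, birth date, smoking history, four comorbidity indices, body mass index and spirometry. Neither document assigns any of these to a model.

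**The concern.** In an observational cohort the groups being compared will generally differ in age, severity and comorbidity. If a factor raises risk but is commoner in younger or milder patients, the two effects oppose each other and the crude comparison can be close to null. An adjusted model would reveal the effect, and the data for it are collected. A sequence that takes forward only what the crude test shows may never fit that model.

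What is at stake is missed associations between patient characteristics and outcome. The argument concerns comparisons between patients. It does not extend to the paired t and McNemar tests, which compare the same patients over time and so are not exposed to this kind of imbalance.

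**Working it through.** **Reading the text.** Three links from crude to adjusted analysis can be set side by side.

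- Bivariate tests to multivariate study: the SAP carries forward associations found in the crude step, so the order is stated.
- Relative risk of future events: adjusted by regression, with no crude-test condition in the sentence. The order is suggested only.
- Log-rank to Cox: Cox is for potential associations, without saying where they were found. The order is suggested only.

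None of the three gives a threshold, names covariates, or says what happens to a crude-null factor.

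**The documents' own figure.** The protocol's Sample size section gives 15 × 4 × 48 = 2880, and 2880 × (1 − 0.20 − 0.20 − 0.10) = 1440. This reproduces. It is a feasibility count, used below only as n.

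**Assumed inputs (none is in the documents).** 35% of patients have the factor (504 against 936). One normal confounder has mean s SD lower in those with the factor. Entry screens of 0.05, 0.10 and 0.20 are tried because none is written. The adjusted test is two-sided at 0.05.

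**Continuous outcome.** True difference 0.16, confounder slope 0.3, within-group SD 1.

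- Crude difference = 0.16 − 0.3s. Crude SE = √(1/504 + 1/936) = 0.0553.
- Chance of passing the screen ≈ Φ(difference/SE − z), with z = 1.96, 1.645 or 1.282.
- Adjusted SE = √(1 − 0.3²) × 0.0553 × √(1 + 0.35 × 0.65 × s²).
- s = 0.2: crude difference 0.10, ratio 1.81, pass 44/57/70%. Adjusted SE 0.0529, ratio 0.16/0.0529 = 3.02, power Φ(3.02 − 1.96) = 86%. Loss at the 0.20 screen: 86 − 70 = 16 points.
- s = 0.4: crude difference 0.04, ratio 0.72, pass 11/18/29%. Adjusted SE 0.0537, ratio 2.98, power 85%.

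Under masking, nearly every cohort that passes the crude screen is also significant when adjusted, so the pass rate approximates the chance of doing both.

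**Binary event.** True OR 1.40, confounder OR 1.6 per SD, reference risk 35%. Crude OR ≈ 1.40 × 1.6^(−s), which is 1.27, 1.16 and 1.06 at s = 0.2, 0.4 and 0.6.

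**Simulation.** 4,000 cohorts of 1440 per setting; Monte Carlo standard error at most √(0.25/4000) = 0.8 points. Entries are the percentage of cohorts in which the factor passes the crude screen and is significant when adjusted.

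| Outcome | s | Screen 0.05 | 0.10 | 0.20 | Always adjusted |
|---|---|---|---|---|---|
| Binary | 0 | 79 | 82 | 83 | 83 |
| Binary | 0.2 | 53 | 66 | 77 | 82 |
| Binary | 0.4 | 24 | 34 | 49 | 80 |
| Binary | 0.6 | 8 | 13 | 21 | 79 |
| Binary | −0.2 (confounding the other way) | 83 | 83 | 83 | 83 |
| Continuous | 0 | 81 | 85 | 86 | 86 |
| Continuous | 0.2 | 43 | 55 | 70 | 86 |
| Continuous | 0.4 | 11 | 18 | 28 | 84 |

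A repeat run at s = 0.2 gave 57/67/77 against 83% (binary) and 44/57/71 against 86% (continuous).

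**Survival, only if the suggested order is applied.** Time runs from inclusion, after the entry rule "Followed up by our team for at least 3 years" is met. A further 3 years of observation, a hazard of 0.07 per year, a true HR of 1.40 and a confounder HR of 1.6 per SD are assumed. At s = 0.2 the result is 55/66/78 against 82%; at s = 0.4 it is 24/35/49 against 79%.

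**The case against.** The strongest reply is that the SAP does not forbid adjusting other factors. The word potential need not mean p < 0.05, and the modelling is left to depend on the analysis in hand. The t and chi-square tests are attached to baseline comparisons, and neither the relative-risk sentence nor the Cox sentence states a screen. The large losses need both a strict screen and a sizeable imbalance, and every input except n is assumed. The protocol's Sample size section also gives building a cohort as the main objective, with no confirmatory hypothesis.

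Much of this stands. A reader might infer that the SAP sets a 0.05 entry rule, or that survival is explicitly screened by the log-rank test. The text supports neither. The size is illustrative, and at a lenient screen with mild masking it is modest for a binary event or survival.

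It does not remove the point. The only order the SAP spells out runs from a crude finding to adjustment, and the broader reading of the other sentences still supplies no covariates and no route for a crude-null factor. As written, the choice would be made after the data are seen.

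**Conclusion.** The point holds as a gap in the analysis plan that is worth closing. If the written sequence is followed, a between-patient factor opposed by confounding may be missed. The loss at mild masking (0.2 SD) and a 0.20 screen is about 5 points for a binary event (82 − 77) and 16 for a continuous outcome (86 − 70). It grows with a stricter screen or stronger masking, is small without confounding, and is nil when confounding runs the other way. These sizes rest on the assumed prevalence, effects and imbalance, and on a single confounder measured without error. They show the mechanism at n = 1440, not a forecast for TRACE.

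A reader might also infer a failure to study treatment response, since the protocol's introduction aims at "the multidimensional behavior of the disease over time and the determinants of the different response to treatments". Whether a factor-by-treatment interaction should be planned is a separate question. It would remain if crude screening were dropped, and it rests on that one statement of aims, so it is not part of this conclusion.

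**What to change.** Add wording to the SAP along these lines: for each between-patient factor studied, the Cox model (or the matching regression for other outcomes) is fitted whatever the bivariate or log-rank p-value. It is adjusted for a core set fixed before analysis from data already collected, for example age, sex, smoking and one named comorbidity index, plus baseline FEV₁ unless it lies on the causal path of that factor. Crude and adjusted estimates are reported with 95% confidence intervals, and the bivariate and log-rank tests are descriptive. Since neither document lists the factors to be studied, that list should be written down at the same time.

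No new data are needed. The cost is a few degrees of freedom, a causal-path decision for each factor, and more models, to be labelled exploratory. False positives sit at about the nominal level instead of below it. In simulation, a truly null factor was declared significant in 5.1–5.3% of cohorts when always adjusted, against 4.1% with a 0.05 screen and no confounding. With a 0.4 SD imbalance the figures were 5.1% against 2.4%.
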